5.5.1 Product Use Pattern

Actual product use pattern categorization is described in Figure 2 below,

Confidentiality Statement

Figure 2: Product Use Categorization

Note: HS: HeatSticks

The calculation of product use categories will be performed based on Figure 2. For each subject we will calculate product use for two time periods, representing Week 1 use and average product consumption from V3 till end of Month 3 or last visit prior to early termination whichever comes first.

- From V3 to V4: Week 1
- From V3 to V43/Last visit before early termination: Overall average consumption

For each time period the daily product use reported by a subject in the study will be summed up and averaged by the actual number of days the subject was in the study after randomization until date of last reported product use within the respective time period. This will then be multiplied by 30 to describe the average monthly product use.

For subjects who early terminated from the study, product use for overall average consumption will be calculated until the last visit prior to V44. For example, if a subject early terminated at V23 and subsequently came for V44, then product use will be calculated from V3 until the date of V23.

As both electronic diaries and paper diaries were used in the study concurrently for some subjects, the following rules will be applied in case of inconsistencies.

Confidentiality Statement

Philip Morris Products SA.	Statistical Analysis Plan	Confidential
P1-EXC-01-EU	Final 2.0	Page 29 of 71
Related to PMI-RRP-WKI-112487		SAP_P1-EXC-01-EU

- When there is data available for both electronic and paper diaries for the same date, the electronic diary data will be kept if both are the same. If the data is different on the same date, then data for this date will be considered missing.
- If a subject reports no product use but a value is recorded, we will assume that the number of product used reported was correct and use it in the derivation of product use.

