Missing data for self-reported daily use will not be imputed and we will assume that the derived average monthly use from non-missing data is representative of the actual usage. For each analysis period (Week 1 or Overall), if more than 50% of product use data is not available then the subject will be grouped into the 'Others' product use arm. Therefore, it is possible that a subject is not considered for statistical modelling as it is grouped into 'Others' for Week 1 (3 out of 7 days of product use data only) but available for analysis for the entire study period if more than 50% of product use data was eventually collected throughout the study. A subject may have switched product use groups throughout the study and the total number of subjects in an arm may fluctuate over time depending on the actual product use.

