8.3 As Exposed Exercise Compliant Set

The As Exposed Exercise Compliant Set (AEECS) consists of all randomized subjects who have at least one valid non-safety assessment after randomization, specifically we have

- post-randomization product (cigarette or IQOS) use experience if randomized to IQOS, • IQOS-2 or cigarette arm or
- no product use if randomized to the SA arm,

and who attended at least 34 of 38 (~90%) of the exercise training sessions except the subjects in IQOS-2 arm. Subjects in the IQOS-2 will be analyzed as exposed as they did not participate in the training. The AEECS will be analyzed by actual exposure (product use exposure, actual study arm).

Due to technical issues with the bike training equipment during the study, these rules are used to determine if a subject completed a training session for the purposes of defining the AEECS analysis set in addition to information regarding whether a training visit was done or not. We define a training session to be completed if a minimum of 20 or more minutes of exercise was done. If the training time is unknown then the session is considered to be not done. These checks from the protocol deviation dataset will be done regardless of whether data from the exercise training is available or not.

For a training session to be considered as not done from the protocol deviations (PD) dataset, the PD description will be checked for the following,

- "Bike training was not done" •
- "Bike training was partially completed for less than 20 min ..."
- "Bike training was partially completed for unknown number of minutes ..."

A bike training session is considered as complete if the following description for bike training is provided in the PD dataset,

- "Bike training was completed..."
- "Bike training was partially completed for at least 20 min..." •

In the case where there are inconsistencies between the PD dataset and bike training data, ie, for example bike training was marked as complete but the PD descriptions says otherwise, the PD rules will be used to determine completion of a bike training session.

Confidentiality Statement

Philip Morris Products SA.	Statistical Analysis Plan	Confidential
P1-EXC-01-EU	Final 2.0	Page 32 of 71
Related to PMI-RRP-WKI-112487		

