8.4 As Exposed Biochemically and Exercise Compliant Set

A subset of the AEECS based on biochemical verification of smoking status (AEBECS) will be analysed based on actual arm as determined with these additional criteria.

For a subject to be classified as smoking abstinent, in addition to the product use diary with an average cigarette use at max 5 Cigarettes/month the following will be used,

- No CO breath test > 6 ppm at three consecutive visits from V3 onwards.
- Total NNAL concentration < 75.9 pg/mL in spot urine (Berg, et al. 2012) at two or more visits collected from V3 onwards.
- CEMA concentration adjusted for creatinine < 40 ng/mg creat (Claussen, et al. 2019) in spot urine at two or more visits collected from V3 onwards.

The following biochemical verification will be used in addition to the product use diary to further fine tune subjects in the IQOS user group.

- No CO breath test > 6 ppm at three consecutive visits from V3 onwards.
- Total NNAL concentration < 75.9 pg/mL in spot urine at two or more visits collected from V3 onwards.
- CEMA concentration adjust for creatinine < 40 ng/mg creat in spot urine at two or more visits collected from V3 onwards.

8.5 **Protocol Deviations**

All protocol deviations will be listed and also summarized based on the classification of deviation type for subjects in the Safety Set.

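### SAP 5.5.1 divides product use by elapsed days, not recorded diary days, so missing or discordant days count as zero use and the averages are understated

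*SAP*

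**What the plan says.** SAP 5.5.1 derives average product use for two periods: Week 1 (V3 to V4) and Overall (V3 to V43, or to the last visit before early termination). In each, reported daily use is summed and "averaged by the actual number of days the subject was in the study after randomization until date of last reported product use", then multiplied by 30.

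The same section sets the missing-data rules:
- Some subjects kept electronic and paper diaries at the same time. "If the data is different on the same date, then data for this date will be considered missing".
- Missing daily use is not imputed, and "we will assume that the derived average monthly use from non-missing data is representative of the actual usage".
- In either period, "if more than 50% of product use data is not available then the subject will be grouped into" the Others group, which SAP 9.4 lists but does not analyse.

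SAP 9.1.4 repeats that missing product use is not imputed. Neither section takes missing days out of the divisor. SAP 5.5.2 and 5.5.3 define further averages for cigarettes and HeatSticks without naming a divisor.

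The average feeds the product-use category, which serves as the analysis arm. For the main non-safety set, SAP 8.3 says: "The AEECS will be analyzed by actual exposure (product use exposure, actual study arm"). SAP 8.2 treats the Safety Set the same way, and SAP 9.1.1 makes actual exposure the main stratification criterion.

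**The concern.** Section 5.5.1 states an aim and a formula that do not agree. An average from non-missing data needs a divisor that counts only days with data. The stated divisor counts calendar days up to an end date, so every gap before that date is scored as a day of no use. This amounts to imputing zero, which the section says it will not do. The SAP foresees such gaps: it describes concurrent diaries that may disagree, and it keeps subjects with up to half their entries missing.

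The error has one direction. Reported consumption looks lower than the diaries show, and more so in subjects with poorer diaries. It enters the product-use summaries directly. It could also reach the exposure arm used in AEECS and the Safety Set, and the compliance analysis in SAP 9.6.2.1, which compares actual with randomized arm. Daily cigarette use is a covariate as well (exploratory in SAP 9.6.1.1.1 and 9.6.1.1.2; fixed in 9.6.1.1.3, 9.6.1.1.4, 9.6.1.1.6 and 9.6.1.1.7). It is affected only if its average uses the same divisor.

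**Working it through.** **Inputs from the SAP.** Overall period 106 days (V43 at 106±2 days after V3, section 4.1). Week 1 is 7±2 days (section 4.1). At most 50% of entries missing, and scaling by 30 (section 5.5.1). Section 8.4 gives a diary limit for abstinence: "average cigarette use at max 5 Cigarettes/month". Using that limit for the categories in Figure 2 is an assumption. The numbers of recorded days and cigarettes below are illustrative.

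**Check on the 50% rule.** The section's own example has 3 of 7 days available, so 4/7 = 57.1% is missing and the subject goes to Others. The rule is consistent with its example.

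**Formulas.** Let n be the recorded total, L the elapsed days to the last diary entry and k the recorded days.
- As written: 30·n/L
- From non-missing data: 30·n/k
- Understatement factor: L/k

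Missing days after the last entry enter neither n nor L, so only earlier gaps matter.

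**Overall period, last entry on day 106.** A total changes side of an assumed 5/month limit when 30n/106 ≤ 5 (n ≤ 17) and 30n/k > 5.

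| Recorded days k | Factor 106/k | Totals that change side |
|---|---|---|
| 101 | 1.05 | 17 |
| 95 | 1.12 | 16–17 |
| 80 | 1.33 | 14–17 |
| 53 (50% limit) | 2.00 | 9–17 |

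Example: 17 cigarettes over 95 recorded days gives 17/106 × 30 = 4.81 as written, against 17/95 × 30 = 5.37 per month.

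A daily smoker does not cross. At one cigarette a day and 53 of 106 days recorded, the rule gives 53/106 × 30 = 15.0 per month.

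**Week 1.** The largest factors the 50% rule allows are 5/3 = 1.67, 6/3 = 2.00, 7/4 = 1.75, 8/4 = 2.00 and 9/5 = 1.80 for periods of 5 to 9 days. In a 7-day period, only a single recorded cigarette with 4 or 5 recorded days and a last entry on day 6 or 7 changes side. As written it gives 30/6 = 5.0 or 30/7 = 4.29; on recorded days it gives 30/4 = 7.5 or 30/5 = 6.0.

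**Alternative end date.** If the end date were the last day with non-zero use, recorded zeros after it would drop out. Two cigarettes by day 3, then no use of any product and zeros recorded to day 106, would give 2/3 × 30 = 20.0 instead of 2/106 × 30 = 0.57 per month. If the end date is the last use of any product, a subject who smokes those two cigarettes and uses HeatSticks to day 106 still gets 0.57.

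**The case against.** **The statement on non-missing data already governs.** It follows the divisor sentence closely, and section 9.1.4 supports it, so a sensible programmer might divide by recorded days. But that statement names no divisor, while the sentence before it names a different one. A programmer who follows the explicit formula gets the understated figure. The conflict stands, though its cure is short.

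**The effect on arms is narrow and unproven.** This stands. A reader might infer that the rule misassigns subjects in the main analysis. The documents do not show that. The cut-offs are in Figure 2, which the text available for review does not reproduce. If the categories rest on the share of cigarettes and HeatSticks, the divisor cancels. Under an assumed count limit, only the small totals tabulated above move. In addition, section 8.3 lists "no product use if randomized to the SA arm" as a condition for AEECS. Read literally, this removes lapsing SA-randomized subjects, leaving near-abstainers randomized to other arms. The allowance in section 8.4, for a subset of AEECS, casts some doubt on so strict a reading but does not exclude it.

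**A large overstatement in quitters.** A reader might also infer this from the end-date wording, partly because the clause "If a subject reports no product use but a value is recorded" could suggest that a no-use day is not a report of use. That reading is weak. The clause settles a conflict between a no-use answer and an entered count. A recorded zero is a reported value, and the reading leaves the divisor undefined for anyone who used nothing, in a trial with an abstinence arm. If the end date is the last use of any product, it affects only subjects who stop everything. It remains a secondary ambiguity.

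**Safeguards exist.** The 50% rule caps the factor at 2.00, more than 50% missing is a major deviation (8.5.1), and daily use is listed (9.5). AEBECS adds exhaled CO, NNAL and CEMA, though it still uses the diary average. FAS is analysed by randomized arm, but section 9.6.1.3 leaves its endpoint analyses to discretion. The study is descriptive, with no hypothesis test.

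**Conclusion.** Wrong as written; minor. The stated divisor turns missing and discordant days before the last diary entry into zero use, against the section's own rule. Average use is understated by the ratio of elapsed to recorded days: 1.12 at 95 of 106 days, 1.33 at 80, and never more than 2.00. This rests on the SAP's wording and arithmetic alone, taking the end date as the last diary entry.

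Any effect on the analysis arm is conditional. It needs a count-based limit in Figure 2; with the 5 cigarettes a month borrowed from section 8.4, only near-abstainers with incomplete diaries could change side. The documents do not allow a count of such subjects, and a check of the divisor against Figure 2 would settle whether there can be any. The documents likewise do not establish that daily smokers are reclassified, that the main comparisons are biased, or that use is greatly overstated in quitters.

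**What to change.** In SAP 5.5.1, divide summed use by the number of days in the period with a valid, concordant diary entry, recorded zeros included, then multiply by 30. Delete the end-date clause from the divisor, which also removes the secondary ambiguity. State the same divisor in 5.5.2 and 5.5.3. Section 9.6.1.1.5 is a precedent: it averages step counts over valid days.

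The cost is one reworded sentence and two added ones, with no new data. Some subjects may change exposure group. Two limits remain. Short periods stay sensitive to completeness: in Week 1, one recorded cigarette gives 4.3, 5.0, 6.0 or 7.5 per month at 7, 6, 5 or 4 recorded days. And neither divisor corrects for days left blank because the subject smoked.

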5.5 Product Use

The number of Cigarettes, Heatsticks, and other nicotine/tobacco containing product used daily, as reported by the subject and collected in the electronic diary or paper CRF, will be used to monitor product use and evaluate adherence to product allocation.

Additionally, BoExp measured in the study will be used to fine tune product use allocation as an exploratory analysis.

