9.1.3.1 Analysis Period

In general, the analysis will be performed at a visit(s) level but in the case where data is collected more frequently for example the Mhealth or exercise training data we define the analysis period by month. Here, Week 1 is the period between V3 and V4, Month 1 is described as the period between V5 up to the date of V14, Month 2 is the day after V14 and until the date of V28 and Month 3 represents the day after V28 until the date of V43.

For certain endpoints (see section 9.6.1.2) related to $VO2_{max}$ and exercise capacity the analysis period Week 1 and Month 3 will have different baseline values dependent on the subject's product use group during the corresponding period for the calculation of the descriptive statistics.

9.1.4 Handling of Dropouts, Missing Data (Including Outside the Limits of Detection or Quantification) or Partial Data

Dropouts (discontinued subjects) and other subjects with missing data will be analyzed in the analysis set(s) when data are available, without imputation of missing data.

No imputation schemes for missing values will be applied.

For laboratory parameters outside the limit of detection or quantification, the following imputation will be performed:

- Values below the lower limit of detection (LLOD) or quantification (LLOQ) will be imputed as 0.5 x LLOD or LLOQ.
- Values above the upper limit of detection (ULOD) or quantification (ULOQ) will be imputed as the ULOD or ULOQ.

The number of values below LLOD (or LLOQ) or above ULOD (or ULOQ) will be presented in each summary table, as well as the statistics on the other quantitative values.

However, if 50% or more data are below the lower limit or above the upper limit, only the number of values below the lower limit and above the upper limit will be reported in the

Confidentiality Statement

Philip Morris Products SA.	Statistical Analysis Plan	Confidential
P1-EXC-01-EU	Final 2.0	Page 36 of 71
Related to PMI-RRP-WKI-112487		

summaries, together with minimum (if no value below the lower limit is present) and maximum (if no value above the upper limit is present) of the observed values, and no other statistics will be reported.

There will be no imputation of missing laboratory parameters.

For product use data that are missing:

• There will be no imputation and all available data (ePRO and/or paper) will be analyzed as is.

For bike training data that is incomplete:

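### SAP 5.5.1 drops every date on which the electronic and paper diaries differ; such dates always carry use of some product, so actual-use grouping can be wrong in either direction

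*SAP*

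**What the plan says.** SAP 5.5.1 deals with a practical problem: "As both electronic diaries and paper diaries were used in the study concurrently for some subjects". When both sources exist for a date, "the electronic diary data will be kept if both are the same"; otherwise, "If the data is different on the same date, then data for this date will be considered missing". The diaries cover several products: "The number of Cigarettes, Heatsticks, and other nicotine/tobacco containing product used daily" (SAP 5.5).

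The cleaned diary yields a monthly average for each product, separately for Week 1 (V3 to V4) and Overall (V3 to V43). One paragraph of 5.5.1 divides summed use by days in the study up to the last report. A later paragraph refers to an average from non-missing data and assumes that it represents actual use. In addition, "if more than 50% of product use data is not available then the subject will be grouped into the 'Others' product use arm". SAP 9.4 lists that group but does not analyse it.

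The resulting category is the analysis group for the AEECS (the main non-safety set), the AEBECS and the Safety Set (SAP 8 and 9.1.1). The cut-offs are in Figure 2, which is not shown in the text available for review. The only legible limit is in SAP 8.4, for abstinence in the AEBECS: "average cigarette use at max 5 Cigarettes/month".

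**The concern.** The rule looks neutral: if the sources disagree, trust neither. It is not neutral, because agreement is guaranteed on a date when both diaries record no use and can fail only when at least one records some. The dates lost are selected by the quantity being averaged.

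The average decides who counts as abstinent, IQOS user, dual user or smoker in the main analysis. The abstinence limit is low, so one date can decide the group. The rule also acts on the date, so a one-stick HeatStick mismatch removes a cigarette count on which both diaries agree. Frequent small mismatches can remove a daily user from the models altogether. SAP 9.6.1.3 and the table list in 13.2 contain no sensitivity analysis for discordant dates.

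**Working it through.** **Inputs.** Scaling by 30, the two denominators and the 50% limit are from SAP 5.5.1. The limit of 5 cigarettes per month is from SAP 8.4; its use in Figure 2 is an assumption. Week 1 is taken as 7 days and Overall as 106 days (SAP 4.1). The chance p that a use day is discordant is not in the documents and is shown over a range.

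Monthly use = 30 × sum / days. Denominator A is all days in the study (a missing day acts as zero). Denominator B is non-missing days only.

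**1. The SAP's own example.** With 3 of 7 days available, 4/7 = 57.1% is missing, which exceeds 50% and gives 'Others', as the SAP states.

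**2. What a deleted date contains.** Let each diary record hold cigarettes, HeatSticks and other products, each from 0 to 3. That gives 64 records and 64 × 63 = 4032 ordered pairs that differ. None has zero use in both diaries. In 16 × 15 = 240, cigarettes are zero in both. These are counts of possible pairs, not frequencies. A deleted date is thus always a use date, but not always a cigarette date.

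**3. How low the limit is.** 5 × 7/30 = 1.2 cigarettes in Week 1; 5 × 106/30 = 17.7 Overall.

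**4. Cigarette counts differ, near-abstinent subject.**
- Week 1, six agreed zero days and one day of 0 versus 2: 0 per month under the rule; 30 × 2/7 = 8.6 if the higher count is kept.
- Overall, 18 cigarettes: 30 × 18/106 = 5.09. Deleting one 1-cigarette date gives 30 × 17/106 = 4.81 (A) or 30 × 17/105 = 4.86 (B).
- Week 1, 1 cigarette on each of 2 days (8.6 per month): one deletion gives 30/7 = 4.3 (A) or 30/6 = 5.0 (B). The chance of falling to 5 or below is 1 − (1 − p)², i.e. 19%, 51% and 75% for p = 0.1, 0.3 and 0.5.
- Overall, 1 cigarette every fourth day (7.5 per month), denominator B: 30 × 0.25(1 − p)/(0.25(1 − p) + 0.75) = 6.9, 5.7 and 4.3 for the same p. It reaches 5 only at p = 0.4.

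**5. Only another product differs, on cigarette-free dates.**
- Week 1, 1 cigarette in 7 days: 30/7 = 4.3. With two such dates deleted, B gives 30/5 = 6.0; A stays at 4.3.
- Overall, 17 cigarettes: 4.81. With five such dates deleted, B gives 30 × 17/101 = 5.05; A stays at 4.81.
- HeatStick share, illustrative week of five days at 10 HeatSticks and 0 cigarettes and two days at 4 and 6: 58/70 = 82.9%. Deleting two cigarette-free dates gives 38/50 = 76.0%; deleting one cigarette date gives 54/60 = 90.0%.

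**6. Loss to 'Others' in Week 1.** For a subject who uses some product daily, the chance that at least 4 of 7 dates are discordant is 0.3%, 13% and 50% for p = 0.1, 0.3 and 0.5, taking days as independent.

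**7. Heavy use.** A smoker at 15 per day stays at 450 per month under B. Under A, even with 52 of 106 dates deleted, the figure is 30 × 15 × 54/106 = 229, far from 5.

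**The case against.** The strongest reply is that the direction of error is not uniform. A reader might infer that the rule always moves IQOS subjects towards exclusive IQOS use. It does not. For someone who uses some product every day, every day is at risk of deletion, so the non-missing average is unbiased if discordance is unrelated to cigarette use. HeatStick mismatches on cigarette-free dates push away from exclusive use (step 5). This stands.

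A reader might also infer that complete abstainers can never be lost. That holds only for subjects who record no product at all. The SA arm may use nicotine replacement (Protocol 6.3.2.3), and a mismatch there, if entered in the diary, deletes the date too.

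Nor is there a clear contradiction elsewhere in the SAP. The next bullet, "If a subject reports no product use but a value is recorded, we will assume that the number of product used reported was correct", addresses a no-use statement alongside a recorded number; it does not say which of two diaries to believe. In SAP 9.1.4, "all available data (ePRO and/or paper) will be analyzed as is" appears under missing product use data and rules out imputation, which is compatible with a date already declared missing.

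Some mitigation exists. FAS analyses by randomized arm do not use diary groups, and VO2max tables for the FAS are listed in 13.2, although 9.6.1.3 makes them discretionary. The AEBECS adds CO, NNAL and CEMA checks but is exploratory. Leaving relapsers in the SA or IQOS groups would, on the CO rationale in Protocol 4.2, tend to dilute contrasts with cigarettes, so the rule cannot be said to favour those products.

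Finally, the text could be read as a product-level comparison. It speaks of the date's data, so deletion of the whole date is the natural reading. On the narrower reading the loss of agreed cigarette counts disappears, but step 4 remains.

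**Conclusion.** The rule makes missingness depend on the value measured, and the representativeness assumption in 5.5.1 does not hold for discordant dates. Where cigarette counts differ in a near-abstinent subject, the error favours classification as abstinent under either denominator. Where only another product differs, a valid cigarette count is discarded and, over non-missing days, the error can go the other way. Many small mismatches can move a daily user to 'Others'.

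One date can change a Week 1 group (0 versus 8.6 per month around a limit of 5). How many subjects this touches is unknown: the SAP gives neither the number with both diaries nor the discordance rate. The examples assume that the limit in 8.4 also applies in Figure 2; the cut-off between IQOS and dual use cannot be checked. With 25 subjects planned per training arm, a few regrouped subjects could matter, but the documents do not show that they will. A blanket claim of bias towards abstinence or exclusive IQOS use is not supported.

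**What to change.** In SAP 5.5.1:
- Compare the two diaries product by product. Keep every field that agrees, and count the date as available for the 50% rule for those products.
- For a product whose counts differ, state one rule that does not delete the day.
- State one denominator, since the two paragraphs of 5.5.1 imply different ones.
- Regroup the AEECS as a sensitivity analysis, using (a) the higher count and (b) the electronic value.
- Report the number of subjects with both diaries and the number of discordant dates, by product.

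The cost is SAP wording and a little programming; no new data are needed. The drawback is that an over-entry in one diary can reclassify a true abstainer under the higher-count analysis (a single erroneous entry of 2 cigarettes in Week 1 gives 8.6 per month). That is why the higher count is proposed here as one of two sensitivity analyses and not as the only rule.
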